## **SCHEMA:**

[figure not shown]
Basal cell carcinoma is a malignancy with significant prevalence that rarely metastasizes but can be locally destructive. Laser therapy for this type of lesion may be a superior option for patients who do not wish to or cannot tolerate other modalities such as topical chemotherapeutics or surgery.

In this pilot study, we will preliminarily assess the efficacy and safety of the 595/1064 nm Multiplex laser when treating superficial and nodular basal cell carcinomas less than 1.5 cm in size. Eligible patients with biopsy-proven superficial or nodular BCCs less than 1.5 cm in size will have the opportunity to enroll in this study. This is an unblinded study in which patients will be randomized to either a treatment arm or a control arm. Patients in the treatment arm will receive three treatments with the 595/1064 nm multiplex laser spaced four weeks apart. In addition to assessing the presence of any adverse effects, photographs will be taken at each visit. One month after the last treatment session, patients in this group will return for evaluation of 1) clinical clearance and 2) histological clearance of their BCC. In order to assess clinical clearance, a dermatologist will grossly examine, measure, and document any residual lesion. Afterwards, a deep excisional biopsy encompassing the entire region will be taken and histological clearance will be determined by a microscopic examination for any residual tumor cells. Follow-up for wound care of the biopsy will occur one week later. Tumor burden will be calculated by change in surface area of the lesion.

After standard diagnostic biopsy, patients in the control arm will be followed for three regular visits, spaced 4 weeks apart. One month after the third follow-up visit, control patients will return for final photography and evaluation of clinical and histological clearance, just as the treatment arm. Although extremely rare, if any clinical signs of progression are visible during this period (what we will consider greater than 10% growth), the patient will be withdrawn from the study and will undergo standard of care treatment.

### **Eligible patients (N=20)**

**Adult patients with superficial or nodular basal cell carcinoma less than 1.5cm in size on either trunk or extremities.**

**HYPOTHESIS:**

The 595/1064 nm Multiplex laser is a potentially safe and effective treatment of superficial and nodular basal cell carcinomas less than 1.5 cm in size.

## **1.0 BACKGROUND**

### **1.1 Study Disease**

Basal cell carcinoma (BCC) is the most common malignant tumor in humans and its incidence is increasing. In the United States alone, approximately 1 million new cases of BCC are diagnosed annually. Basal cell carcinomas rarely metastasize but can be locally destructive and invasive over a long period of time. Rates of growth, however, are small and successful treatment has been found to not be compromised by waiting an average of 10 weeks for elective excision. Superficial (17.4%) and nodular (21%) subtypes, moreover, are considered very common. Numerous treatments such as surgical excision, cryotherapy, topical imiquimod, 5-fluorouracil, curettage and electrodesiccation, and Mohs micrographic surgery currently exist. A number of patients, however, cannot tolerate the inflammatory response associated with topical immunomodulators nor the surgical approaches that are known to lead to high clearance rates. Furthermore, some of the current treatment alternatives for BCC, most notably including surgical excision and Mohs micrographic surgery, have a high risk of pain, scarring, or increased healing time, as well as greater risk for infection.

Basal cell carcinomas are considered highly vascular lesions. Basal cell tumor beds have been found to be enclosed by a dense capillary network and basal cell carcinomas are very often characterized by superficial telangiectasias. In addition, superficial and nodular basal cell carcinomas may contain melanin, possibly giving these lesions a brown, blue or black hue.

### **1.2 Study Agent**

The Cynosure 595/1064 nm Cynergy multiplex laser is a combination laser emitting both 595 nm and 1064 nm wavelengths, corresponding to visible and infrared regions of the electromagnetic spectrum, respectively. It is capable of delivering one wavelength pulse alone or sequentially delivering two pulses, one of each wavelength. The laser's "MultiPlex technology" allows the wavelengths to be sequentially administered in a controlled and safe manner.

The 595 nm aspect of this laser is currently indicated for benign vascular and vascular dependent lesion removal. The 1064 nm wavelength is currently indicated for the coagulation and hemostasis of benign and vascular lesions such as, but not limited to, port wine stains, hemangiomas, warts, telangiectasias, rosacea, venus lakes, leg veins, spider veins and poikiloderma of Civatte, in addition to treatment of benign cutaneous lesions such as age and solar lentigos, café au lait macules, seborrheic keratoses, nevi, chloasma, verruca, skin tags, keratoses, tattoos, and plaques.

Using the 595 nm and 1064 nm lasers sequentially creates a synergistic effect. The first pulse with the 595 nm wavelength laser generates the chromophore methemoglobin, which diffuses more deeply into the dermis and is readily targeted by light from the second pulse (1064 nm wavelength laser). This allows for both increased efficacy and the ability to use lower fluences for each wavelength, increasing safety.

### **1.3 Other Agent(s)**

N/A

### **1.4 Rationale**

Due to the fact that basal cell carcinomas are highly vascular lesions and tumors on the whole are known to be dependent on blood supply, we propose that using the 595/1064 nm Multiplex laser, with wavelengths known to target both superficial and dermal blood vessels, will result in clearance of the basal cell carcinoma by destroying the lesion's blood supply. In addition, these wavelengths are also able to target pigment, which may be present within basal cell carcinoma as well.

### **1.5 Gender and Ethnicity**

N/A

## **2.0 OBJECTIVES**

This is a pilot study to determine whether there is potential for the development of a larger clinical trial to properly evaluate whether the 595/1064 nm multiplex laser is a safe and effective treatment for superficial and nodular basal cell carcinomas less than 1.5 cm in size.

### **2.1 Primary objectives**

The primary objective of the study is to preliminarily assess the efficacy of the 595/1064 nm multiplex laser for the treatment of superficial and nodular basal cell carcinomas less than 1.5 cm in size.

Efficacy will be measured both clinically and histologically. This will first be determined by clinical dermatologic evaluation for the gross appearance of residual lesion. Residual tumor burden will be calculated by change in surface area of the lesion. Histological clearance will be determined by absence of residual tumor cells on histopathology of biopsy following treatment. The primary endpoint is response, defined as CR or PR. (see Section 9).

## **2.2. Secondary objectives**

The secondary objective of this study is to assess the safety and side effect profile of the multiplex laser for this indication.

Although the 595/1064 nm multiplex laser has been deemed safe when used for other dermatologic conditions, this will be the first time this combination laser will be used specifically in the context of treatment for superficial and nodular basal cell carcinomas. We do not anticipate an increased risk of adverse effects in this clinical context, however, we intend to thoroughly monitor for and document any new and/or concerning adverse reactions to the multiplex laser. During treatment, any adverse events that occur will be documented. Furthermore, at each visit, patients will be questioned about whether any side effects occurred after treatment and in the period leading up to the next session.

## **3.0 PATIENT SELECTION**

### **3.1 Inclusion Criteria**

3.1.1 Adults age 18 years or older

3.1.2 Diagnostic biopsy must be no later than three months prior to enrollment

3.1.3 Lesion is biopsy-proven nodular or superficial BCC

3.1.4 BCC is 1.5 cm or less in diameter

3.1.5 BCC is on trunk or extremities

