### **3.2 Exclusion Criteria**

3.2.1 BCC is greater than 1.5 cm in size

3.2.2 If location of BCC is on the face.

3.2.3 Patients whose biopsy shows a subtype other than superficial or nodular, or has characteristics of a more aggressive nature, such as:

- Basosquamous basal cell carcinoma
- Morpheaform/ infiltrative basal cell carcinoma
- Sclerosing basal cell carcinoma
- Recurrent basal cell carcinomas

3.2.4 Patients who may not be able to tolerate light therapy, such as:

- Patients with seizure disorders triggered by light
- Patients who have or are currently receiving gold therapy
- Patients with any light sensitive disorder
- Patients taking medication that increases sensitivity to light (see appendix VI)
- Patients with Systemic Lupus Erythematosus

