3.2.5 Fitzpatrick skin types V or VI

3.2.6 Patients who are taking certain oral medications such as:

- Isotretinoin (currently or within last 6 months)
- Medications that alter wound healing (see appendix VI)

3.2.7 Patients who have a history of Herpes Simplex Virus outbreak in the area to be treated

- 3.2.8 Patients whose lesion has been previously, or is currently being, treated by another modality (topical immunomodulators/ chemotherapeutics, cryotherapy, curettage and electrodesiccation, surgical excision, or Mohs micrographic surgery)

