## 5.0 CLINICAL AND LABORATORY EVALUATIONS

### 5.1 Baseline/pretreatment evaluation

Prior to involvement in the study

Prior to consideration of being a possible participant in the study, patients will receive a diagnostic biopsy as is the standard practice for evaluation of lesions that are suspicious for BCC.

Patients that present to [name] clinic for follow-up of their biopsy who have biopsy proven superficial or nodular basal cell carcinoma will be approached to participate in the study. We will identify patients who have biopsy proven superficial or nodular basal cell carcinoma on the trunk or extremities that is less than 1.5 cm in size via medical records (partial waiver

of authorization approval). If patients have more than one BCC that satisfy inclusion criteria, they will also be treated.

After signing informed consent, patients will be fully evaluated for eligibility criteria. Patients will be randomly assigned in either a control arm or treatment arm. Patients will be advised that if placed in control arm, there is an extremely low risk of serious progression during the short time needed for the study and that should any clinical signs of progression be seen, they would be withdrawn from the study and receive immediate surgical excision.

Patients will be entered into Velos system and completed HIPAA forms will be sent to HIPAA privacy office as per University of Miami policy.

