### 9.2 Response Criteria

For determination of response, we will consider:

- Complete response (CR):

- 1) Both clinical and histological disappearance of the target lesion or
- 2) Positive clinical assessment of the "lesion" but negative histology.

- Partial response (PR):

- 1) At least 10% decrease in the size of lesion on clinical evaluation and positive histology or
- 2) Complete clinical clearance of the lesion and positive histology.

- Progression of disease : At least 10% increase in the size of the lesion on clinical evaluation.

- Stable disease (SD): Clinically, neither sufficient reduction to qualify for PR nor sufficient increase to qualify for PD.

The following table summarizes the above response criteria.

		Clinical assessment			
Histology		No lesion	Lesion ≤90% baseline size	Lesion >90 but <110% baseline size	Lesion ≥110% baseline size
	Positive	PR	PR	SD	PD
	negative	CR	CR	SD*	PD*

\* not expected to occur.

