### APPENDIX I: STUDY CALENDAR

Procedure	Screening	Randomization 	Day 0	Day28 (+/- 7 days)	Day 56 (+/- 7 days)	Day 84 (+/- 7 days)	Day 91 (+/- 7 days)/ Follow up visit
Written Informed Consent	X						
HIPAA	X						
Photo consent	X						
Eligibility checklist 	X						
Velos	X						
Randomization		X					
Pt and lesion characteristics 			X	X	X	X	

Treatment #1 			X				
Treatment #2 				X			
Treatment #3 					X		
Photographs are taken			X	X	X	X	
Monitoring of adverse events and concomitant medication			X	X	X	X	X
Dermatologic eval for clearance						X	
Excisional biopsy						X	

Within 3 months of initial diagnostic biopsy and within 1 week of enrollment (+ 3 days)

 Source document titled "Enrollment"

 Source document titled "Patient information"

 Or regular study visit for control arm

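### Eligibility does not require a measurable lesion to remain after the diagnostic biopsy, so a biopsy-cleared site can enter and score as a complete response in either arm

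*Combined protocol and SAP*

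**What the plan says.** - **Biopsy before entry.** Section 5.1 states that, before being considered, "patients will receive a diagnostic biopsy as is the standard practice for evaluation of lesions that are suspicious for BCC". Section 3.1 gives the pathology and timing rules as "3.1.3 Lesion is biopsy-proven nodular or superficial BCC" and "3.1.2 Diagnostic biopsy must be no later than three months prior to enrollment".
- **Size.** The inclusion rule is "3.1.4 BCC is 1.5 cm or less in diameter" and the matching exclusion is "3.2.1 BCC is greater than 1.5 cm in size". Both are upper limits. Neither section mentions a minimum size, visible residual lesion or biopsy margins.
- **Prior treatment.** Section 3.2.8 excludes "Patients whose lesion has been previously, or is currently being, treated by another modality" and lists therapies. Diagnostic biopsy is not on the list.
- **Order of events.** Section 5.1 finds candidates, including by size, through medical records. Eligibility is evaluated after consent and before assignment, and Section 3.3.2 requires a signed checklist before randomization. In Appendix I the row "Pt and lesion characteristics" is first marked on Day 0, after the randomization column, as are photographs. Section 3.3.3 says the trial is unblinded.
- **Endpoint.** The first route to complete response in Section 9.2 reads "Both clinical and histological disappearance of the target lesion or", followed by a second route for a clinically apparent lesion with negative histology. The table in 9.2 scores no lesion with negative histology as CR. Sections 2.1 and 13.1 make CR plus PR the primary endpoint.

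**The concern.** A diagnostic biopsy of a lesion no larger than 1.5 cm may take out much or all of it. If nothing is left, the subject still has a biopsy-proven BCC and still meets the upper size limit. At Day 84 the site shows no lesion and clean histology, and it is scored as a complete response that the laser did not cause.

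Two results are at stake. One is the laser arm's response rate, the figure a reader will carry forward from a pilot meant to show whether the laser merits further study. The other is the comparison with control, which has only five evaluable subjects to show how often untreated sites clear. The baseline area is also the denominator for the 10% response and progression thresholds, and its first scheduled measurement comes when the arm is already known.

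**Working it through.** **1. A cleared lesion followed through the rules.** It meets 3.1.3 on the biopsy specimen, 3.1.4 because there is no lower limit, and 3.1.2 if the biopsy was recent enough. It is not excluded by 3.2.1 or 3.2.8. At Day 84 both arms have clinical and histological assessment (Sections 4.0 and 5.3), and the 9.2 table gives CR. With zero baseline area, the percentage change planned in 13.3 and the 90% and 110% columns in 9.2 have no defined value.

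**2. The plan's own figures.** One-sided Fisher tests for 15 versus 5 subjects give 0.0578 (11 v 1), 0.0307 (12 v 1) and 0.0298 (9 v 0). These match the 0.058, 0.031 and 0.030 in Section 13.2.

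**3. What the test needs.** For one-sided p < 0.05 the laser arm needs at least 9 responders with 0 control responders, 12 with 1, and 14 with 2. With 3 or more control responders no result is significant (15/15 v 3/5 gives p = 0.053). Going from no control response to one therefore changes the result only when the laser arm has 9, 10 or 11 responders.

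**4. Effect of clearance.** Let q be the share of enrolled lesions already cleared by biopsy. It is not in the documents, so a range is assumed. Let p = 11/15 be the laser response in residual lesions, which is the lower end of the sponsor's expectation in 13.2. Assume that residual lesions in control do not respond and that each subject has one BCC.

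- Control rate = q
- Laser rate = q + (1 − q)p
- Difference = (1 − q)p
- Chance of at least one control CR among five = 1 − (1 − q)^5
- Expected cleared lesions in the laser arm = 15q
- Power = sum over both binomials of the outcomes with one-sided Fisher p < 0.05

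| q | Laser rate | Control rate | Difference (points) | At least 1 control CR | 15q | Power |
|---|---|---|---|---|---|---|
| 0 | 73.3% | 0% | 73.3 | 0% | 0 | 92% |
| 5% | 74.7% | 5% | 69.7 | 23% | 0.75 | 82% |
| 10% | 76.0% | 10% | 66.0 | 41% | 1.5 | 73% |
| 20% | 78.7% | 20% | 58.7 | 67% | 3.0 | 59% |
| 40% | 84.0% | 40% | 44.0 | 92% | 6.0 | 38% |

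Example for q = 10%: 0.10 + 0.90 × 0.733 = 0.760, and 1 − 0.9^5 = 0.41.

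The pattern does not depend on p = 11/15. For the same values of q, power runs 61.0%, 54.3%, 48.1%, 37.5%, 23.5% with p = 60%, and 98.2%, 90.7%, 83.7%, 70.8%, 46.7% with p = 80%.

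**5. Inert laser.** If the laser does nothing, both arms respond at rate q. The test then rejects in less than 0.01% of trials at q = 10%, 0.03% at 20%, 0.26% at 30% and 0.79% at 40%.

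**The case against.** The strongest reply is that the protocol presupposes a lesion. The criteria are in the present tense, Section 9.1 is headed as measurable disease, complete response speaks of a target lesion disappearing, and 11.4 lets the investigator withdraw a subject for whom treatment is inappropriate. Many investigators would not enrol an empty site. This makes such entries less likely, but none of it is an eligibility rule and the response table does not enforce it.

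A reader might also infer four stronger things that the documents do not support.

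- **That nothing is known about size before randomization.** Size is an eligibility item and the checklist is signed first. Section 4.0 also refers to ruler measurement at an initial evaluation. What is missing is a scheduled measurement at screening: the size may come from records, and the timing of that initial evaluation is not fixed.
- **That an ineffective laser could look effective against control.** Controls have the same biopsy history and the same Day 84 assessment, so clearance appears in both arms. Step 5 shows rejection below 1%.
- **That any single control clearance overturns the result.** The sponsor's own table shows 12/15 v 1/5 is significant, so this holds only at 9 to 11 laser responders.
- **That development turns on a set threshold for the laser arm alone.** Eleven or more of fifteen is an expectation. No go/no-go threshold is stated.

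It is also fair to say that the effect's size rests on an assumed rate, and that wound contraction passing for shrinkage cannot be quantified from the documents. Section 9.1 directs measurement at residual tumor, so I give that route no weight.

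**Conclusion.** The point holds as a gap in the eligibility rules and in the timing of the baseline measurement. Written as it is, the plan can admit biopsy-cleared sites and count them as complete responses in either arm. The laser arm's own rate is then biased upward, and the between-arm comparison is diluted. The direction holds for any clearance rate above zero. The size is conditional on that rate: with 11/15 response in residual lesions, even 5% clearance costs about ten points of power (92% to 82%), and 20% costs about a third of it (92% to 59%). This assumes one BCC per subject, no response in untreated residual lesions, and equal clearance in both arms on average. With five controls, chance imbalance can be large.

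The 92% row is a reference with no cleared lesions, not a promise of what a new criterion would restore. A visible lesion can still be histologically negative, as the second route to CR in Section 9.2 recognizes.

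**What to change.** Add to Section 3.1, applied to each lesion where a subject has several, a clinically visible residual lesion that is distinct from the biopsy scar and measurable in two perpendicular diameters. Any minimum size is for the sponsor to set, since the documents give no basis for one.

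In Appendix I, move the first ruler measurement and photograph to screening, before randomization. Confirm the 1.5 cm limit from that measurement and use it as the baseline for Section 9.1.

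The change costs one eligibility line and one measurement and photograph taken earlier. Some screened patients will not be enrolled, and accrual will be slightly slower. It will reduce biopsy-cleared entries without removing all of them, so the control arm's clearance should still be read alongside the laser arm's rate.

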3.1.6 Fitzpatrick skin types I, II, III, or IV

3.1.7 Female subjects should either be:

- Post-menopausal as defined by 12 months with no menses without an alternative medical cause.

- Surgically sterile, by means of a hysterectomy, or

- Females of child bearing potential must agree to use “highly effective” method of birth control as defined by FDA that result in low failure rate (i.e. <1% per year) and include:

- Intrauterine device

- Hormonal contraceptives (oral, depot, patch, injectable, or vaginal ring)

- Sexual abstinence
- Vasectomized partner

3.1.8 Ability to understand and the willingness to sign a written informed consent document

### **3.2 Exclusion Criteria**

3.2.1 BCC is greater than 1.5 cm in size

3.2.2 If location of BCC is on the face.

3.2.3 Patients whose biopsy shows a subtype other than superficial or nodular, or has characteristics of a more aggressive nature, such as:

- Basosquamous basal cell carcinoma
- Morpheaform/ infiltrative basal cell carcinoma
- Sclerosing basal cell carcinoma
- Recurrent basal cell carcinomas

3.2.4 Patients who may not be able to tolerate light therapy, such as:

- Patients with seizure disorders triggered by light
- Patients who have or are currently receiving gold therapy
- Patients with any light sensitive disorder
- Patients taking medication that increases sensitivity to light (see appendix VI)
- Patients with Systemic Lupus Erythematosus

3.2.5 Fitzpatrick skin types V or VI

3.2.6 Patients who are taking certain oral medications such as:

- Isotretinoin (currently or within last 6 months)
- Medications that alter wound healing (see appendix VI)

3.2.7 Patients who have a history of Herpes Simplex Virus outbreak in the area to be treated

- 3.2.8 Patients whose lesion has been previously, or is currently being, treated by another modality (topical immunomodulators/ chemotherapeutics, cryotherapy, curettage and electrodesiccation, surgical excision, or Mohs micrographic surgery)

### **3.3 Recruitment, enrollment, and randomization**

#### **3.3.1 Recruitment**

Patients that present to [name] clinic for follow-up of their biopsy who have biopsy proven superficial or nodular basal cell carcinoma will be approached to participate in the study. We will identify patients who have biopsy proven superficial or nodular basal cell carcinoma via medical records (via partial waiver of authorization approval).

